### 5. SUBJECT ELIGIBILITY

To be eligible to participate in this study candidates must meet the following eligibility criteria within 5 weeks of Study Day 1 or at the time point specified in the individual eligibility criterion listed.

#### 5.1 Inclusion Criteria

1. Must have given written informed consent (signed and dated) and any authorizations required by local law and be able to comply with all study requirements
2. Males or females aged  $\geq 18$  and  $\leq 70$  years old at the time of informed consent
3. Plasma TG at Screening  $> 150$  mg/dL and at qualification of  $> 150$  mg/dL
4. Documented history of hepatic steatosis as determined by at least one imaging record (CT scan, MRI, FibroScan, or US) suggesting liver fat  $> 8\%$ , or positive ultrasound at Screening
5. Baseline MRI indicating hepatic fat fraction (HFF)  $> 8\%$
6. Clinically confirmed diagnosis of T2DM
  - a. Hemoglobin A1c  $> 6.5$  and  $\leq 10\%$  at Screening
  - b. On a stable dose of oral glucose-lowering medication (i.e. metformin, sulfonylureas, DPP-4 inhibitors, SGLT2 inhibitors) for at least 3 months before Screening and plan to remain on the same medication for the duration of the study
7. Body mass index between 27- 40 kg/m^2, inclusive, at Screening
8. If taking lipid lowering medication, subjects must be on a stable dose for at least 3 months before first dose of Study Drug and plan to remain on the same medication for the duration of the study

9. Females: must be non-pregnant and non-lactating and either;
  - a. surgically sterile (e.g., tubal occlusion, hysterectomy, bilateral salpingectomy, bilateral oophorectomy) or;
  - b. post-menopausal (defined as 12 months of spontaneous amenorrhea in females > 55 years of age or, in females ≤ 55 years, 12 months of spontaneous amenorrhea without an alternative medical cause and FSH levels in the postmenopausal range for the laboratory involved) or;
  - c. Abstinent\* or;
  - d. if engaged in sexual relations of child-bearing potential, agree to use 2 highly effective contraceptive methods (refer to [Section 6.3.1](#)) from the time of signing the informed consent form until at least 13 weeks after the last dose of Study Drug (ISIS 703802 or placebo)

\* Abstinence is only acceptable as true abstinence, i.e., when this is in line with the preferred and usual lifestyle of the subject. Periodic abstinence (e.g., calendar, ovulation, symptothermal, post-ovulation methods), declaration of abstinence for the duration of a trial and withdrawal are not acceptable methods of contraception

10. Males must be surgically sterile or, if engaged in sexual relations with a female of child-bearing potential, the subject must be using an acceptable contraceptive method (refer to [Section 6.3.1](#)) from the time of signing the informed consent form until at least 13 weeks after the last dose of ISIS 703802

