	
7. Body mass index between 27- 40 kg/m^2, inclusive, at Screening
 
8. If taking lipid lowering medication, subjects must be on a stable dose for at least 3 months before first dose of study drug and plan to remain on the same medication for the duration of the study
 
9. Females: must be non-pregnant and non-lactating and either;
 

a. surgically sterile (e.g., tubal occlusion, hysterectomy, bilateral salpingectomy, bilateral oophorectomy);

b. post-menopausal (defined as 12 months of spontaneous amenorrhea in females > 55 years of age or, in females ≤ 55 years, 12 months of spontaneous amenorrhea without an alternative medical cause and FSH levels in the postmenopausal range for the laboratory involved);

c. Abstinent* or;

d. if engaged in sexual relations of child-bearing potential, agree to use 2 highly effective contraceptive methods (refer to Section 6.3.1) from the time of signing the informed consent form until at least 13 weeks after the last dose of Study Drug (ISIS 703802 or placebo)

 
* Abstinence is only acceptable as true abstinence, i.e., when this is in line with the preferred and usual lifestyle of the subject. Periodic abstinence (e.g., calendar, ovulation, symptothermal, post-ovulation methods), declaration of abstinence for the duration of a trial and withdrawal are not acceptable methods of contraception
 
10. Males must be surgically sterile or, if engaged in sexual relations with a female of child-bearing potential, the subject must be using an acceptable contraceptive method (refer to Section 6.3.1) from the time of signing the informed consent form until at least 13 weeks after the last dose of ISIS 703802
 
Exclusion Criteria
 

1. Type 1 diabetes mellitus

2. Active chronic liver disease, alcoholic liver disease, Wilson's disease hemochromatosis, primary biliary cirrhosis, primary sclerosing cholangitis, genetic hemochromatosis, known or suspected hepatocellular carcinoma, history of or planned liver transplant for end-stage liver disease of any etiology

3. Documented history of advanced liver fibrosis

4. History of cirrhosis and/or hepatic decompensation including ascites, hepatic encephalopathy, or variceal bleeding

5. Uncontrolled hypertension (systolic > 160 or diastolic > 100 mm Hg)

6. History of acute kidney injury within 12 months of Screening

7. Active infection requiring systemic antiviral or antimicrobial therapy that will not be completed prior to Study Day 1

8. Subjects with a history of major bleed or high-risk of bleeding diathesis

9. Clinically-significant abnormalities in screening laboratory values that would render a subject unsuitable for inclusion, including the following:

a. Positive test (including trace) for blood on urinalysis. In the event of a positive test, eligibility may be confirmed with urine microscopy showing ≤ 5 red blood cells per high power field

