### 3. EXPERIMENTAL PLAN

#### 3.1 Study Design

This is a Phase 2 multicenter, randomized, double-blind, placebo-controlled, dose-ranging study. Approximately 96 subjects will be randomized in a 3:1 ratio to receive ISIS 703802 or placebo. The sample size was determined to provide statistical power for efficacy assessments. Study Drug (ISIS 703802 or placebo) will be administered SC every week or every 4 weeks, depending on cohort assignment, for 26 weekly doses, or 6 every 4-week doses.

Subjects will be evaluated for study eligibility during Screening and Qualification, which takes place up to 5 weeks prior to Day 1 (the first day of Study Drug administration). During the Screening Period, subjects will be advised to maintain routine diet and exercise routines and remain on a stable regimen of diabetes and lipid medications (if they are already taking any). As part of the Screening Period, following 4 weeks of diet run-in, subjects will have a qualification visit and, final eligibility assessments will be performed. Subjects on a stable diet known to the investigator and followed at the site may go from Screening to qualification without a 4-week diet run-in. At the qualification visit, TGs will be measured to qualify ( $\geq 150$  mg/dL). MRI will be obtained during screening once all other eligibility criteria are met to assess liver fat content.

Subjects meeting eligibility criteria at Screening and having a qualifying MRI, defined as having greater than 8% liver fat assessed by MRI-PDF (via central reviewer) will return to the clinic on Day 1. TG and MRI results must be available prior to randomization and administration of the first dose of Study Drug. Subjects who continue to meet all eligibility criteria at Day 1 will be randomized to 1 of the 3 dosing cohorts, with each cohort having a 3:1 ratio to receive ISIS 703802 or matching volume of placebo, respectively, by SC injection.

The primary safety and efficacy analysis time point is at Week 27 for subjects who received weekly dosing (Cohort A) and at Week 25 for subjects who received every 4-week dosing (Cohorts B and C).

Cohort A (n = 32): 20 mg ISIS 703802 or placebo (3:1) SC once every week for 26 doses.

Cohort B (n = 32): 40 mg ISIS 703802 or placebo SC (3:1) once every 4 weeks for 6 doses.

Cohort C (n = 32): 80 mg ISIS 703802 or placebo SC (3:1) once every 4 weeks for 6 doses.

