## **6.3 Restriction on the Lifestyle of Subjects**

### **6.3.1 Contraception Requirements**

All male subjects and women of childbearing potential must refrain from sperm/egg donation and either be abstinent† or practice effective contraception from the time of signing the informed consent form until at least a period of 13 weeks after their last dose of study treatment.

Male subjects engaged in sexual relations with a female of child-bearing potential must also encourage their female partner to use effective contraception from the time of signing the informed consent until a period of 13 weeks after the subject's last dose of study treatment.

For the purposes of this study, women of childbearing potential are defined as any female who has experienced menarche, and who does not meet one of the following conditions:

- Postmenopausal: 12 months of spontaneous amenorrhea in females > 55 years of age or, in females ≤ 55 years, 12 months of spontaneous amenorrhea without an alternative medical cause and FSH levels in the postmenopausal range for the laboratory involved
- 6 weeks after surgical bilateral oophorectomy with or without hysterectomy
- Post hysterectomy

For the purposes of the study, effective contraception is defined as follows:

For male subjects:

- Effective male contraception includes a vasectomy with negative semen analysis at follow-up, or the use of condoms together with spermicidal foam/gel/film/cream/suppository
- Male subjects with partners that are pregnant must use condoms as contraception to ensure that the fetus is not exposed to the Study Drug

For female subjects and female partners of male subjects:

- Using 2 of the following acceptable methods of contraception: surgical sterilization (e.g., bilateral tubal ligation), hormonal contraception, intrauterine contraception/device, or any 2 barrier methods (a combination of male or female condom\* with diaphragm, sponge, or cervical cap) together with spermicidal foam/gel/film/cream/suppository

†**Note:** Abstinence is only acceptable as true abstinence, i.e., when this is in line with the preferred and usual lifestyle of the subject. Periodic abstinence (e.g., calendar, ovulation, symptothermal, post-ovulation methods), declaration of abstinence for the duration of a trial and withdrawal are not acceptable methods of contraception.

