**Appendix A Schedule of Procedures – Weekly Dosing *Continued***

Study Week	Screening r		Treatment Period												Follow-up Period			
	Run-in #	Qual *	1	1	5	9	13	17	21	25	26			27/ET	4*	8*	13*	
Study Day	-5 to -1	-1 to 0	1	2 a	29	57	85	113	141	169	176	177 a	178 a	183	* Weeks from the end of treatment period q			
Visit and Testing Window +/- Days	0	0	0	0	2	2	2	3	3	3	3	0	0	3	3	3	3	
Liver Biomarkers			X				X		X					X			X	
Plasma PK - ISIS 703802 l			X 	X 	X	X	X	X	X		X 	X 	X 	X	X	X	X	
Anti-ISIS 703802 Antibodies			X		X	X	X		X					X	X		X	
FSH (women only, if applicable) j, m	X																	
Serum Pregnancy Test m	X		X		X	X	X	X	X	X				X	X	X	X	
Archived Serum & Plasma Samples j, n			X			X		X	X					X	X	X	X	
PD Panel and phospholipids j	X	X	X		X	X	X	X	X		X			X	X	X	X	
Extended Lipid Panel j	X	X	X		X	X	X	X	X		X			X	X	X	X	
HbA1C j	X		X				X							X			X	
FPG, and delipidated free glycerol, insulin j	X		X		X	X	X	X	X		X			X	X	X	X	
Biomarkers of Inflammation			X				X							X			X	
Study Drug: SC Injection			EVERY WEEK SUBCUTANEOUS ADMINISTRATION OF STUDY DRUG (Week 1 through Week 26/Day 176) o															
Adverse Events	X		X	X	X	X	X	X	X	X	X	X	X	X	X	X	X	X
Concomitant Medication	X		X	X	X	X	X	X	X	X	X	X	X	X	X	X	X	X

† Qual =Qualification

# Subjects on stable diet known to the investigator and followed at the site may go from Screening to qualification without the diet run-in period.

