## Appendix A Schedule of Procedures – Weekly Dosing *Continued*

All procedures and study samples are to be done pre-dose at respective visits, unless specified

- a Visit only required for subjects in PK subgroup.
- b Full physical exam will be performed at the Screening visit and an abbreviated physical exam will be performed during treatment and follow-up periods.
- c Height only required at Screening.
- d MRI will only be performed during Screening after all other eligibility criteria are met. MRI should be performed 10 days (+/- 2 days) prior to anticipated Day 1 date to allow time for result reporting and analysis.
- e All tests listed in [Appendix B](#) under Extended Urinalysis should be performed, including routine urinalysis, urine microscopy, UACR and UPCR.
- f Assessments and procedures to be conducted by either a home healthcare service or the Study Center. Subject Study Center visits must be no more than 4 weeks apart during the treatment period
- g Urine samples for renal biomarkers will be collected. Sample analysis will be conducted in accordance with Safety Monitoring for Renal Function ([Section 8.5.2](#)).
- h During follow-up period, hematology sampling for platelet values are taken every 14 days (+/- 2 days) for 5 weeks after last dose of Study Drug, then at Week 8 and Week 13 Follow-up visits.
- i Serum Creatinine and Cys-C will be collected as a part of chemistry panel at visits when chemistry panel is performed, or as stand-alone samples at time points when a chemistry panel is not performed.
- j Blood samples to be collected after an overnight fast of at least 10 hours and preferably not more than 12 hours, unless tests are repeated for safety reasons.
- k If the platelet value, serum creatinine or liver enzyme tests are uninterpretable (e.g., due to clumping, hemolysis or quantity not sufficient) a repeat blood specimen should be re-drawn as soon as possible (ideally within 7 days). All platelet count results will be reviewed promptly (within 48 hours of receipt) by the Investigator as per [Section 6.2.1](#). Any case of a platelet count  $\leq 50,000/\text{mm}^3$  should be reported in an expedited fashion to the Sponsor.
- l Refer to [Appendix C](#) for PK Sampling schedule.
- m Women who are not surgically sterile or post-menopausal.

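### Footnote m, read with criterion 9a, takes premenopausal women with tubal occlusion or bilateral salpingectomy out of the serum pregnancy test row, although Section 6.3.1 counts them as of childbearing potential

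*Protocol*

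**What the plan says.** Three parts of the protocol bear on who is tested for pregnancy.

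- **Eligibility.** Criterion 9 (Section 5.1) requires every woman to be non-pregnant and to fit one of four categories. The first, 9a, is "surgically sterile (e.g., tubal occlusion, hysterectomy, bilateral salpingectomy, bilateral oophorectomy) or". The synopsis gives the same list.
- **Childbearing potential.** In Section 6.3.1, "women of childbearing potential are defined as any female who has experienced menarche, and who does not meet one of the following conditions". Three conditions follow: postmenopausal, 6 weeks after bilateral oophorectomy, and post hysterectomy. The same section treats tubal sterilization as a contraceptive method, of which two are needed: "Using 2 of the following acceptable methods of contraception: surgical sterilization (e.g., bilateral tubal ligation), hormonal contraception, intrauterine contraception/device", or barrier methods.
- **Testing.** In both Appendix A tables the Serum Pregnancy Test row carries footnote m: "Women who are not surgically sterile or post-menopausal". The FSH row carries it too. The footnote cites neither criterion 9a nor Section 6.3.1.

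Pregnancy is a mandatory reason to stop Study Drug (Section 8.8).

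**The concern.** The test row should cover the women the protocol regards as able to become pregnant. Footnote m uses a different term from Section 6.3.1, and the only list under that term for women is wider than the Section 6.3.1 exemptions. Site staff who apply footnote m by way of 9a would leave out a woman with a tubal procedure who still has her uterus and ovaries.

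What is at stake is safety, not the analysis. Other women of childbearing potential are tested on a schedule, and Appendix A says "All procedures and study samples are to be done pre-dose at respective visits, unless specified". For this woman, a pregnancy during dosing would come to light only if someone suspected it, and further doses could be given meanwhile. Section 2.3.4 reports a terminal half-life of 3 to 5 weeks, so exposure would continue after the last such dose.

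**Working it through.** **Step 1: compare the definitions.** The rows below assume a premenopausal woman with no other exempting condition.

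| Procedure | Surgically sterile (9a) | Exempt from childbearing potential (6.3.1) | In test row (footnote m read with 9a) |
|---|---|---|---|
| Hysterectomy | yes | yes | no |
| Bilateral oophorectomy | yes | yes, from 6 weeks | no |
| Tubal occlusion | yes | no | no |
| Bilateral salpingectomy | yes | no | no |

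The last two rows are the mismatch: of childbearing potential, yet outside the test row.

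**Step 2: count the scheduled tests (Appendix A).**

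- Cohort A: Day 1 and Weeks 5, 9, 13, 17, 21, 25 and 27/ET = 8, plus follow-up Weeks 4, 8 and 13 = 3. From Day 1: 8 + 3 = 11.
- Cohorts B and C: Day 1 and Weeks 5, 9, 13, 17, 21 and 25/ET = 7, plus 3 in follow-up. From Day 1: 7 + 3 = 10.
- Each table also has one test at Screening, under the same footnote.

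**Step 3: count the tests that could prevent a later dose.** Section 6.2 sends all samples to a central laboratory by overnight courier and expects alerts within 2 days of collection. I assume hCG results take about as long, so a test cannot normally stop the dose given at the same visit. At target days:

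- Cohort A, last dose Day 176: tests on Days 1, 29, 57, 85, 113, 141 and 169 all precede a later dose, so 7.
- Cohorts B and C, last dose Day 141: tests on Days 1, 29, 57, 85 and 113 precede a later dose. The Day 141 test coincides with the last dose, so 5.
- The remaining 11 - 7 = 4 and 10 - 5 = 5 tests can detect a pregnancy but cannot prevent a dose.

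On the 9a reading, the affected woman has 0 of 11 or 0 of 10 tests from Day 1, and 0 of the 7 or 5 that could prevent a dose.

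**Step 4: look for another provision that restores scheduled testing.**

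- Section 3.1: "Subjects who continue to meet all eligibility criteria at Day 1 will be randomized to 1 of the 3 dosing cohorts". This rechecks criterion 9, but no test is specified.
- Appendix B lists serum hCG among the screening tests without restriction, and SAP Section 3.5.2 lists it for women. At most this adds one test at Screening.
- Section 9.5.4 provides a test when pregnancy is suspected.

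None of these schedules a test during treatment.

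**The case against.** The strongest reply is that nothing has certainly been omitted. Footnote m does not cite 9a, 9a is a list of examples inside an eligibility criterion, and Section 6.3.1 gives a study-wide definition that a site could apply to the test row. The error could also lie in Section 6.3.1: 9a calls tubal procedures sterilizing, and Section 6.3.1 itself uses the words surgical sterilization for tubal ligation. On that view her omission from serial testing is deliberate. This stands in part. The exclusion depends on a reading, and the documents do not say which text should yield. But the texts conflict as written, and nothing reconciles them.

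A reader might also infer three stronger claims that the documents do not support:

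- *That she goes without contraception.* Section 6.3.1 requires women of childbearing potential to be abstinent or to use two methods, and Section 9.5.4 refers back to it. A tubal procedure counts as one method, so a second is still needed.
- *That every missed test is a missed chance to prevent a dose.* After allowing for laboratory turnaround, 7 and 5 could do so. In Cohort A dosing is weekly and tests are mostly 4 weeks apart, so women who are tested also receive doses between tests.
- *That criterion 9a must be rewritten.* Changing it adds no test, and a non-abstinent woman who declines a second method would become ineligible at entry.

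**Conclusion.** The point holds as an inconsistency in a safety procedure. Read with 9a, footnote m leaves a narrow group of women of childbearing potential with none of the 11 or 10 scheduled tests from Day 1, including the 7 or 5 that could prevent a later dose. This rests on three assumptions: that surgically sterile in footnote m has its 9a meaning, that hCG results follow the general laboratory turnaround, and that visits fall on target days.

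The absolute risk is likely small. Harm would require abstinence, or the tubal procedure and the second method together, to fail without anyone suspecting pregnancy. The documents give neither the number of women affected nor a pregnancy probability, so no risk is calculated. Power, endpoints and the efficacy analysis are unaffected. The case for acting rests on the purpose of the row and the low cost of correcting it.

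**What to change.** In both Appendix A tables, give the Serum Pregnancy Test row its own footnote: *women of childbearing potential as defined in Section 6.3.1*. Leave footnote m on the FSH row, and leave criterion 9a unchanged.

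This is one wording edit in each of two tables. It adds up to 11 hCG assays per affected woman in Cohort A and up to 10 in Cohorts B and C from Day 1, plus at most one at Screening. No extra visit or blood draw is needed. In Cohort A the Extended Lipid Panel is already drawn at 10 of the 11 visits and the Chemistry Panel at Week 25; in Cohorts B and C the Extended Lipid Panel is drawn at all 10. Blood is also drawn at Screening. Eligibility does not change.

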## 5.2 Exclusion Criteria

1. Type 1 diabetes mellitus
2. Active chronic liver disease, alcoholic liver disease, Wilson's disease hemochromatosis, primary biliary cirrhosis, primary sclerosing cholangitis, genetic hemochromatosis, known or suspected hepatocellular carcinoma, history of or planned liver transplant for end-stage liver disease of any etiology
3. Documented history of advanced liver fibrosis
4. History of cirrhosis and/or hepatic decompensation including ascites, hepatic encephalopathy, or variceal bleeding
5. Uncontrolled hypertension (systolic > 160 or diastolic > 100 mm Hg)
6. History of acute kidney injury within 12 months of Screening
7. Active infection requiring systemic antiviral or antimicrobial therapy that will not be completed prior to Study Day 1
8. Subjects with a history of major bleed or high-risk of bleeding diathesis
9. Clinically-significant abnormalities in screening laboratory values that would render a subject unsuitable for inclusion, including the following:

- a. Positive test (including trace) for blood on urinalysis. In the event of a positive test, eligibility may be confirmed with urine microscopy showing  $\leq 5$  red blood cells per high power field
  - b. Urine protein/creatinine ratio (UPCR)  $\geq 0.25$  mg/mg. In the event of a UPCR above this threshold, eligibility may be confirmed by a quantitative total urine protein measurement of  $< 300$  mg/24-hr
  - c. Estimated GFR  $< 60$  mL/min/1.73 m^2 (as determined by the Chronic Kidney Disease-Epidemiological Collaboration (CKD-EPI) Equation)
  - d. Alanine aminotransferase (ALT) or aspartate aminotransferase (AST)  $> 2$  x ULN
  - e. Bilirubin  $> ULN$ , unless prior diagnosis and documentation of Gilbert's syndrome in which case total bilirubin must be  $\leq 3$  mg/dL
  - f. Alkaline phosphatase (ALP)  $> 1.5$  x ULN
  - g. Platelet count  $< LLN$
10. Known history of or positive test for human immunodeficiency virus (HIV), hepatitis C or chronic hepatitis B
  11. Uncontrolled hyper- or hypothyroidism. Subjects on dose stable replacement therapy for at least 3 months prior to Screening will be allowed
  12. History of clinically significant acute cardiac event within 6 months before Screening (includes stroke, transient ischemic attack, and coronary heart disease [angina pectoris, myocardial infarction, revascularization procedures])
  13. History of heart failure with NYHA greater than Class II
  14. Current acute or chronic inflammatory disease
  15. Hypersensitivity to the active substance or to any of the excipients
  16. Active untreated mental disorder or depression. Subjects who are on a stable dose of medication (excluding atypical antipsychotics) for at least 6 months before Screening and whose treating physicians consider them to be mentally stable may be enrolled
  17. Any major surgery including bariatric surgery within 3 months of Screening
  18. Weight change  $> 5\%$  within 3 months before Screening or during diet run in period
  19. Currently taking parenteral or chronic oral corticosteroids, amiodarone, tamoxifen, obeticholic acid, atypical antipsychotics, HIV protease inhibitors, or ursodeoxycholic acid
  20. Alcohol consumption  $> 21$  units of alcohol per week for men and  $> 14$  units of alcohol per week for women over a two year time frame prior to the Baseline MRI eligibility (One drink "unit" or one standard drink is equivalent to a 12 ounce beer, a 4 ounce glass of wine, or a 1 ounce shot of hard liquor)
  21. Malignancy within 5 years, except for basal or squamous cell carcinoma of the skin or carcinoma *in situ* of the cervix that has been successfully treated
  22. Use of warfarin or other coumarins, direct thrombin inhibitors or Factor Xa inhibitors

23. Use of anti-platelet therapies unless the dose has been stable for 4 weeks prior to the first dose of ANGPTL3-LRx and will remain on a stable regimen through the end of the Post-Treatment Follow-up Period, during which regular clinical monitoring will be performed
24. Use of Insulin or insulin analogs, GLP-1 agonists, and PPAR $\gamma$  agonists (pioglitazone or rosiglitazone)
25. Treatment with another investigational drug, biological agent, or device within 1 month of Screening, or 5 half-lives of investigational agent, whichever is longer
26. Treatment with any non-Akcea/non-Ionis oligonucleotide (including small interfering ribonucleic acid [siRNA]) at any time or prior treatment with an Ionis oligonucleotide or siRNA within 9 months of Screening. Subjects that have previously received only 1 dose of an Ionis oligonucleotide as part of a clinical study may be included as long as  $\geq 4$  months have elapsed since dosing
27. Blood donation of 50-499 mL within 30 days of Screening or of  $> 499$  mL within 8 weeks of Screening
28. Unwillingness to comply with study procedures, including follow-up, as specified by this protocol, or unwillingness to cooperate fully with the Investigator
29. Subjects with conditions contraindicated for MRI procedures including subjects who have any metal implant (e.g., heart pacemaker, rods, screws, aneurysm clips) that contraindicates MRI procedures.
30. Have any other conditions, which, in the opinion of the Investigator or Sponsor would make the subject unsuitable for inclusion, or could interfere with the subject participating in or completing the Study

